14.0 Risks to Participants

Since the study involves no invasive procedures, there will be no physical risks to study participants. The consideration of need is potentially stressful, and thus there are possible psychological risks for the caregiver. However, the research team has considerable experience providing psychosocial support to dementia caregivers on various protocols and serious psychological risks are unlikely to occur based on this experience. The potential social or legal risks for the participants relate only to possible violations of confidentiality. Given the procedures outlined below, such risks are highly unlikely.

The experience of the research team and the exclusion of caregivers with serious psychiatric illness will minimize the possibility of psychological risks. The unlikelihood of such problems is evident from the absence of any clinically significant problems during

PROTOCOL TITLE: Care to Plan: Preliminary Efficacy of a Tailored Resource for Family Members of Persons with Dementia

the past 12 years that the research team has operated various protocols related to dementia caregiving intervention research. The research coordinator and research assistant will be trained to interview in ways that are non-threatening, friendly, and respectful. We will emphasize to all participants that they do not have to complete any question they do not want to answer, and that the interview may be terminated at any time according to their wishes. We will stress to ADRD caregivers that their decision to discontinue the study will in no way affect the services they are receiving from the University of Minnesota, RHS, or other entities.

In the event a caregiver does become upset during the interview process, the research coordinator or research assistant will contact [name], who will be available for consultation. If a caregiver is in crisis because of their care situation or some other reason, research staff will be instructed to consult with [name]. With the caregiver's permission, we will then contact the appropriate resource person in an external agency (e.g., the Alzheimer's Association). Based on the research team's experience working with their caregiving families, we expect very few or no such instances to occur. If a member of the research team does identify neglect or other potentially inappropriate care practices, Virginia Adult Protective Services will be notified to protect the rights of persons with dementia and their families.

All information obtained from the participants will remain strictly confidential and will not be released except at the express written request of the study participant. All electronic data will be maintained in Qualtrics, the Secure Computing Environment, secure Academic Health Center project folder, and in Box. All data on [name] computer in [name] and the research staff's computers (also located in [name]) are encrypted and protected by strong passwords only accessible to [name] and the research team.

The CtP tool will be created by the University of Minnesota Health Sciences Technology and hosted on a secure PHR/PHI-compliant server; data can be accessed by the study team via the Secure Computing Environment portal (for those that complete CtP with a provider/care navigator as a part of the study). *Note: While the CtP tool used to capture data inputted, as of February 2021, the data inputted will only be captured and saved to the secure environment for those who complete with an guide/input an ID number.* A summary-sheet of assessment responses and zip code/region-specific resources generated by Care to Plan may be saved to Box (from a Riverside Health password-protected computer) and/or printed to give to the participant as needed. Other resources or recommendations may be provided by the Senior Care Navigators as a part of the routine Riverside Health consultation process. The UMN study team would not have access to Riverside Health medical records.

Research data will be maintained on the Academic Health Center secure project folder for approximately 2-3 years which is the time anticipated it will take to disseminate any

PROTOCOL TITLE: Care to Plan: Preliminary Efficacy of a Tailored Resource for Family Members of Persons with Dementia

and all research papers or presentations from these data. Similarly, paper forms of the data will be located in a locked file cabinet in [name] only accessible to the research team. Unless the data are being filed or accessed, these cabinets will remain locked.

15.0 Incomplete Disclosure or Deception

Not applicable

16.0 Potential Benefits to Participants

16.1 Potential Benefits

We believe participation in both Phase I and Phase II will yield benefits for participants. Utilization of CtP will provide dementia caregivers with improved ability to identify supportive services that are tailored to their needs. Caregivers will be paid up to \$100 following their participation in the study. See above for details related to compensation.

17.0 Data Management

17.1 Data Analysis Plan:

Phase I quantitative analyses: Specific Aim 1. As the Phase I aim is to examine the feasibility, acceptability, and utility of CtP within the partnering RHS sites, the quantitative analyses of the R21 phase will largely rely on descriptive statistics. Specifically, Phase I quantitative analyses will utilize frequency tables and means to examine sample characteristics and item-level responses to the CtP review checklist.

Phase II quantitative analyses: Specific Aim 2. Logistic regression analyses will determine whether participation in the CtP treatment group results in utilization of caregiver support programs over the 6-month evaluation period when compared to ADRD caregivers in the control group. Care to Plan treatment vs. control group membership will be the independent variable of interest; caregiver use of CtP recommended services will serve as the dependent variables.

Additional variables will serve as covariates, including time-invariant and time-varying measurements of stress process covariates. Odds ratios will be examined in order to determine the degree to which these variables explain the observed effects of CtP on dependent variable occurrence. Data available at baseline, 3 months, and 6 months will allow for descriptive and growth curve analyses of rate of change in key outcomes: caregiver efficacy and caregiver distress.^{16,17} The individual growth curve model conceives of development, or change, as the function of an individual growth curve plus random error. In our outcome evaluations, the baseline value will be included as a covariate and time will be “centered” at 6-months post-baseline. We will specifically examine whether individual growth parameter estimates have significant variance around the

PROTOCOL TITLE: Care to Plan: Preliminary Efficacy of a Tailored Resource for Family Members of Persons with Dementia

mean trajectories of change in key dependent variables, and then determine whether treatment group assignment influences outcome change parameters in these models. IBM SPSS 21 will be utilized to conduct the within-subject growth curves; the PI has extensive experience conducting growth curve/trajectory analyses.¹⁸⁻²⁴ An additional advantage of this approach is its ability to incorporate missing longitudinal data points, given assumptions of missing at random.²⁵

Variations in CtP use and sex as a biological variable. Empirical utility/feasibility data and context of care measures that assess heterogeneity in the use of CtP within the treatment condition (e.g., frequency and duration of CtP use) as well as degree of contact with CtP interventionists across treatment and control groups will explore the effects of these variations on key study outcomes. Caregiver gender will also be included to examine whether women or men caregivers are more likely to indicate acceptability of CtP and report significant increases or decreases in the hypothesized outcomes following CtP use over a 6-month period.

Phase I and Phase II qualitative analyses. Analyses of acceptability and feasibility across Phases I and II will focus on thematic content analysis of open-ended data to examine CtP utility and mechanisms of benefit. Qualitative analytic techniques described by Morse and others^{26,27} will be used. These approaches allow participants to construct meanings, perceptions, and behaviors from their own vantage points. All open-ended data collected will be read by study's dissemination team to identify textual elements that emerge repeatedly (i.e., codes); these codes will then be clustered into larger categories that are later used to construct major thematic elements from the text (with the use of nVivo 11 analytic software). These themes will provide insights as to CtP's implementation as well as use and mechanisms of benefit in both Phases I and II. During weekly meetings [name], the research coordinator, and the research assistant will discuss their own identified codes to reach a consensus.

Phase II mixed methods analysis. Additional mixed methods analyses^{28,29} will take place during Phase II. The thematic codes and categories of implementation/use and mechanisms of benefit will be cross-tabulated with the empirical data from the randomized controlled evaluation to determine whether the findings diverge, converge, or highlight pathways toward additional questions and analysis.²⁸ This comparative, mixed method analysis approach will inform why or why caregivers do not experience benefit when using CtP.

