#9: 16662	X	3/19/20	Modification of telephone-based consent form to include additional information (i.e. mandated reporting of vulnerable adult abuse, ClinicalTrials information, & data storage information)	Yes
#10, 11, 12: Discarded	-	-	-	-
#13: 17283	2 (V3)	4/15/2020	1. Update to reflect hard copy form availability if needed, 2. Change of study end-point to reflect use of CtP services (not frequency of use), 3. As desired/needed, participant may review online tool simultaneously with care navigator, 4. Ensure accurate terminology regarding the RHS contact referral process/outreach, 5. Update incentive payment process in regards to the semi-structured interview; 6. Uploaded Riverside staff training certificates to IRB/Ethos	Yes
#14: 17595	X	5/3/20	Update to permission to contact form to allow for inputting both name of person obtaining permission for contact and name of person completing the form.	X
#15: 18063	X	6/3/2020	Add [name], research assistant, to project	X
#16: 18430	3 (V4)	6/25/2020	Uploading of Phase II consent form (designed to mimic the phase I consent form, with	Yes

PROTOCOL TITLE: Care to Plan: Preliminary Efficacy of a Tailored Resource for Family Members of Persons with Dementia

MOD #	Protocol Revision #	Version/Submission Date	Summary of Changes	Consent Change?
			updates to study delivery), surveys, and recruitment ads. Protocol update clarifies screening process for contacts who reach out to UMN directly and recruitment section updated to include Riverside Intranet.	
#17: 5971	4 (V5)	8.24.2020	Modification to adverse event section to create a more robust Data Safety Monitoring Plan; clarification of processes for "usual care" control group for Phase II; clarification of process for selection of Phase II final phone interviews/process for analysis; minor updates to surveys; removal of 6 month CtP checklist; addition of disposition surveys for Phase II; submission of phase II advertisements and cover letters (minor edits ongoing as needed); removal of coaching manual on ethos (integrated into online tool); adding online URL for CtP tool to protocol and screen shots of tool/recommendations to Ethos; clarification of study withdrawal/termination by PI.	Yes
#18: Discarded	-	-	-	-
#19: 19666	X	9/3/2020	CtP tool recommendations updated 9/2/2020; list of updated resources uploaded to Ethos for record; CtP tool navigator tip added to	X

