3.0 Study Endpoints/Events/Outcomes

- 3.1 Primary Endpoint/Event/Outcome: Caregiver self-efficacy
- 3.2 Secondary Endpoint(s)/Event(s)/Outcome(s): Caregiver distress (role captivity, role overload, loss of intimate exchange, depressive symptoms); Use of CtP-recommended services

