10.0 Study Population

10.1 Inclusion Criteria:

The care recipient has received a provider diagnosis of Alzheimer's disease or a related dementia (ADRD); and 2) the caregiver is 21 years of age or older; 3) English-speaking; 4) self-identifies as someone who provides help to the person with ADRD because of their cognitive impairments; 5) the caregiver indicates a willingness to use Care to Plan (CtP); and 6) caregiver resides in one of 4 Riverside Health regions (based on zip code). *Note: For study purposes, a diagnosis of mild cognitive impairment is considered along with related dementia diagnoses for study inclusion.*

10.2 Exclusion Criteria: Those who do not meet the inclusion criteria above are not eligible. Additionally, those who endorse a history of a serious mental health disorder whose: a) symptoms have exacerbated in the last six months, and b) are not receiving steady, ongoing pharmacological or other treatment for these symptoms, will be excluded from the project.

10.3 Screening:

To facilitate recruitment and enrollment in both phases of the project, RHS staff (e.g., RHS clinic management, social worker, Senior Care Navigator, or other staff) will present details about the CtP R21 study over the telephone. Those caregivers that express interest and agree to be contacted about the study are referred to the Riverside Senior Care Navigation project team, who securely share their contact information with the UMN research team ([name], the UMN research coordinator, and the research assistant). The inclusion criteria listed above will then be

PROTOCOL TITLE: Care to Plan: Preliminary Efficacy of a Tailored Resource for Family Members of Persons with Dementia

applied via a telephone-screening procedure by the UMN research coordinator or research assistant. Interested contacts that contact UMN staff directly will have the same screening and eligibility procedures applied. If eligible, the UMN research coordinator or research assistant will then describe the study process to an eligible caregiver, and proceed to the consent procedures.

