13.0 Recruitment Methods

13.1 Recruitment Process:

Riverside Health System (RHS) was selected as a site for the proposed R21 due to the ethnically, racially, and geographically diverse population of older adults served. The Senior Care Navigation case management program; a geriatric assessment clinic; a memory café program, an evidence based caregiver intervention program; and other RHS services will serve as sources of recruitment. Riverside staff (within and outside the project staff) may call/share information about the project via phone to their clients as desired (i.e. when waiting for appointments, etc.). Interested contacts will have their contact information securely transferred to study staff. Other sources of recruitment may include Riverside Center for Excellence in Aging and Lifelong Health outreach; radio interviews; community organizations and events; Riverside or community leadership; letters to providers to share information about the study; the Riverside Intranet; newspaper advertisements; and other IRB-approved flyers (electronic/hard copy), print ads, e-mail, newsletters, and social media (i.e. Instagram, Facebook, Twitter, LinkedIn, etc.) ads. Registration forms for educational presentations (by study staff or other agencies) may include an opportunity for individuals interested to provide their permission for the research team to contact them to share additional information about the study. *[Thus, by nature of this, UMN staff or other agency staff involved in planning, hosting, or post-webinar certificates will have access to the names/contact information of those indicating interest in receiving more information about the study].* Presentation “polls” may offer an additional opportunity for presentation attendees to provide permission for contact. Presentation slides may also be used during these community presentations to increase outreach. Hard copy permission forms may also be presented at in-person presentations. Ads/approved presentation slides may also be displayed online/electronically via

PROTOCOL TITLE: Care to Plan: Preliminary Efficacy of a Tailored Resource for Family Members of Persons with Dementia

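### The Phase II service-use endpoint does not separate services newly started after randomisation from services already in use, so the uptake effect may be diluted

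*Combined protocol and SAP*

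**What the plan says.** Section 3.2 lists the secondary endpoint as "Use of CtP-recommended services", without a definition, a time window or a rule on new versus continuing use. Section 17.1 asks whether "participation in the CtP treatment group results in utilization of caregiver support programs over the 6-month evaluation period" and specifies logistic regression, in which "caregiver use of CtP recommended services will serve as the dependent variables".

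For covariates, Section 17.1 states: "Additional variables will serve as covariates, including time-invariant and time-varying measurements of stress process covariates". Baseline service use is not named. Adjustment for the baseline value of the outcome appears later in the same section, in the text on growth curves for caregiver efficacy and distress.

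On recruitment, Section 13.1 names the Senior Care Navigation case management program and a geriatric assessment clinic, and continues: "a memory café program, an evidence based caregiver intervention program; and other RHS services will serve as sources of recruitment". It then adds wider routes: "Other sources of recruitment may include Riverside Center for Excellence in Aging and Lifelong Health outreach; radio interviews; community organizations and events". Section 10 has no criterion on current service use. Its exclusion text says "Those who do not meet the inclusion criteria above are not eligible" and adds only a mental-health exclusion. The stratified enrolment in the Phase II Procedure concerns caregiver gender.

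**The concern.** The question in Section 17.1 is causal: does CtP lead caregivers to take up support? A service that a caregiver had started before randomisation was not started because of CtP. If its continuation scores as use, existing users tend to score as successes in both arms whatever their assignment. The comparison then rests on the remaining caregivers, while the denominator includes everyone.

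This matters because Section 17.2 gives the purpose of Phase II as generating power estimates for a larger trial. A diluted uptake effect could be read as little benefit on this endpoint, or carried into the next sample size without anyone knowing how much of it reflects use that was already in place.

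**Working it through.** **Inputs from the documents.** Phase II enrols 100 caregivers, randomised 1:1 (Phase II Procedure), with 10% attrition at 6 months (Section 17.2). This gives 100 × 0.9 / 2 = 45 per arm.

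**The plan's own figure.** Section 17.2 claims sufficient power for a medium/large effect but gives no alpha, no power and no numeric effect size, and it concerns the growth-curve outcomes. With an assumed two-sided alpha of 0.05 and 80% power, the detectable standardised difference is (1.960 + 0.842) × √(2/45) = 0.59, which is compatible with the claim. There is no stated figure for service use to reproduce.

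**Assumptions.** The documents give no service-use rates. I assume new uptake among baseline non-users of u = 25% (control) and 50% (CtP), an odds ratio of 3.0. I take f, the share already using a listed service at baseline, as 20–40%, and assume that every existing user scores as a user. Tests are two-sided at 0.05.

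**If continuing use counts.** Each arm's rate becomes p = f + (1 − f)u, so the risk difference is (1 − f)(0.50 − 0.25).

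Power = Φ[(d − 1.96·se0)/se1], where d is the risk difference, se0 = √(2p̄(1 − p̄)/n) and se1 = √((pC(1 − pC) + pT(1 − pT))/n).

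Example at f = 0.20:
- pC = 0.20 + 0.80 × 0.25 = 0.40; pT = 0.20 + 0.80 × 0.50 = 0.60; d = 0.20.
- Odds ratio = (0.60/0.40)/(0.40/0.60) = 2.25.
- se0 = √(2 × 0.25/45) = 0.1054; se1 = √(0.48/45) = 0.1033.
- Power = Φ[(0.20 − 0.2066)/0.1033] = 47%.

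**If only new use among baseline non-users is analysed.** The rates stay at 25% v 50%, with n = 45(1 − f) per arm. At f = 0.20, n = 36, se0 = 0.1141 and se1 = 0.1102, so power = Φ[(0.25 − 0.2237)/0.1102] = 59%.

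| f | Control v CtP, continuing use counted | Risk difference | Odds ratio | Power | Odds ratio, new use | Power, new use |
|---|---|---|---|---|---|---|
| 20% | 40% v 60% | 20 points | 2.25 | 47% | 3.0 | 59% |
| 30% | 47.5% v 65% | 17.5 points | 2.05 | 39% | 3.0 | 54% |
| 40% | 55% v 70% | 15 points | 1.91 | 31% | 3.0 | 47% |

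**Other assumed rates, at f = 40%.**
- 20% v 50%: odds ratio 4.0 falls to 2.15; power 42% against 64% for new use.
- 30% v 60%: odds ratio 3.5 falls to 2.29; power 44% against 61%.
- 20% v 40%: odds ratio 2.67 falls to 1.64; power 21% against 36%.

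**Adjustment instead of restriction.** In simulation at 25% v 50%, with 90% of baseline users assumed to continue, adjusting for baseline use gained roughly 10 points of power over the unadjusted comparison at the same f.

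**The case against.** A reader might infer that the plan scores any use during the 6 months. It does not say so. The revision log has "Change of study end-point to reflect use of CtP services (not frequency of use", but that entry is only context and does not settle new versus continuing use. What the documents show is an undefined rule under which continuing use could count.

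A reader might also infer that the effect is certainly pulled toward the null. That requires both arms to be scored on a common list. CtP recommendations are individual (Section 4.0), and controls do not complete CtP during the 6 months. If use were scored against each person's own recommendations, controls would have none to use, and the distortion would run away from the null. This part of the objection stands, and it makes the definition more necessary.

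Recruitment is only partly through support programs. Section 13.1 also lists a clinic, media and community routes, and nothing in the documents shows that the memory café or Senior Care Navigation is itself a CtP-recommended service. So f is unknown and could be small.

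Three further points stand:
- A chance imbalance in baseline use after randomisation is not bias. It is already reflected in the confidence interval and the type I error.
- The fair power comparison is at the same f. Setting 31–47% against the 69% that 45 per arm would give with no existing users overstates what the fix can recover.
- A consultation may help a caregiver stay with a service, so an any-use effect is a legitimate quantity. It answers a different question from uptake.

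Finally, the surveys are not in the documents, and the covariate list in Section 17.1 is not exhaustive. Baseline use may be recorded, and the model could include it. The plan does not commit to either, so the gap in the analysis text remains.

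**Conclusion.** The point holds conditionally. The plan does not define service use as new uptake and names no baseline-use adjustment for the logistic model, and existing users can enrol. If continuing use counts and both arms are scored on a common list, the risk difference shrinks by (1 − f) and the odds ratio moves toward 1. Under the main assumed rates, at f = 20–40%, the odds ratio is 1.91–2.25 instead of 3.0. Analysing new use gains about 12–16 points of power at the same f, although power stays below 60% either way.

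The size rests on assumed rates, an assumed f, and every existing user scoring as a user. The documents do not support a claim of confounding or a fixed direction of bias. The endpoint is secondary and the primary outcome, self-efficacy, is unaffected. The change is still worth making, because it is cheap and the estimate is meant to inform a larger trial.

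**What to change.** 1. Score service use in both arms against one common list of service types, not against each person's own CtP recommendations.
2. Make the analysed outcome a service type newly started after randomisation, meaning one that the caregiver did not report using at baseline. At minimum, enter baseline service use in the logistic model. If nearly all baseline users score as users, ordinary logistic regression may fail through near-complete separation, so name a stratified or penalised method in advance.
3. Report baseline service use by arm, and keep any use over 6 months as a descriptive table.

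The cost is analysis-plan wording, plus one baseline item if the survey lacks it. There will be fewer events, because continuing use no longer counts. The power figures above are for baseline non-users only. Scoring by service type would also let existing users contribute when they start a different type, and its power was not calculated. If baseline use was not collected, state the possible dilution as a limitation on the estimate passed to the larger trial.
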